6.5 Follow-Up Assessments

For post-randomisation follow-up, patients in **both the treatment and control arms** will have **Ca19.9 measurement** and clinical review (including **physical examination**, **weight**, **vital signs** and **assessment of ECOG performance status**, **haematology & biochemistry**):

- Every 3 months for the first year
- Every 6 months for the second year

In addition all patients will have a CT scan of the chest, abdomen and pelvis:

Every 6 months for the first 2 years

After this 2 year follow-up period, all patients will then have Ca19.9 measurement, assessment of Performance Status, and a CT scan of the chest, abdomen and pelvis:

Every 12 months up to 5 years

NOTE: "Additional scans may be carried out at the Investigator's discretion". The protocol CT scan schedule should be followed until disease recurrence is documented. After recurrence is documented, CT scans should continue at the Investigator's discretion and according to normal local practice

For the first 5 years post-randomisation, all patients will be followed up as indicated above. However patients should also still be followed up as is routine practice at each centre. After the 5 year period, all patients should be followed up until death, according to routine practice. All patients will be flagged at the Office of National statistics (ONS).

6.6 Guidelines for Management in the Event of Disease Recurrence

Patients in either arm who develop recurrent disease may be treated at the discretion of the investigator. The patients may be offered chemotherapy including recruitment into the trial ABC02.

6.7 Quality of Life Assessment

A named person at each participating centre must be nominated to take responsibility for the administration, collection and checking of QoL questionnaires. The QoL questionnaires (and the BILCAP health problems questionnaire – see below) will be collated into a QoL & Health Economics booklet to be given to patients to complete. The questionnaire booklet will be handed out to the patient by the Investigator or study nurse at the hospital /clinic.

Once the patient has consented to participate in the trial, the first QoL assessment will be taken prior to randomisation. After this, QoL assessments will be taken at each follow-up visit during the first 2 years of follow-up (or for as long as the patient remains well enough to attend the clinic).

There are 3 versions of the QoL & Health Economics booklets (a, b & c), to be completed as follows:

- Version a (baseline): to be completed by patients prior to randomisation
- Version b (follow-up during first year): to be completed by patients at each 3-monthly follow up visit during the first year (i.e. at 3, 6, 9 & 12 month post-randomisation)
- Version c (follow-up during second year): to be completed by patients at each 6-monthly follow-up visit during the second year (i.e. at 18 & 24 months post-randomisation)

The patient will be asked to fill out the questionnaires as completely and accurately as possible. The average time to complete the entire questionnaire booklet is approximately 15-20 minutes.

6.8 Health Care Economics Assessment

The treatment arm and control arm are expected to differ in costs. Additional information on supportive care, including additional treatment, will be recorded on patient case report forms

(CRFs). The BILCAP health problems questionnaire (included in the QoL booklet, see above) will be used for additional health care evaluation.

7 SAFETY REPORTING & MONITORING

7.1 Adverse Events Definitions

Adverse Event (AE): any untoward medical occurrence in a patient receiving treatment according to the study protocol and which does not necessarily have a causal relationship with the protocol treatment.

Adverse Reaction (AR): all untoward and unintended responses to an investigational medicinal product (IMP) related to any dose administered. An AE judged by either the reporting Investigator or Sponsor as having causal relationship to the IMP qualifies as an AR. The expression reasonable causal relationship means to convey in general that there is evidence or argument to suggest a causal relationship.

Unexpected Adverse Reaction (UAR): an AR, the nature or severity of which is not consistent with the applicable product information (i.e. the Summary of Product Characteristics (SPC) for capecitabine which is a licensed product). When the outcome of an AR is not consistent with the applicable product information the AR should be considered unexpected.

Serious Adverse Event (SAE) or Serious Adverse Reaction (SAR):

Any untoward medical occurrence or effect that at any dose:

- · Results in death*
- Is life-threatening**
- Results in persistent or significant disability/incapacity
- Requires hospitalisation or prolongation of existing hospitalisation***
- Is a congenital anomaly/birth defect discovered during the study period
- Is a new primary cancer

Medical judgement should be exercised in deciding whether an AE or AR is serious in other situations. An AE or AR that is not immediately life threatening or does not result in death or hospitalisation, but may jeopardise the subject or may require medical or surgical intervention to prevent one of the other outcomes listed above (excluding cancer), should be considered serious.

^{*} Except death due to biliary tract cancer

^{**} The term 'life threatening' in the definition of an SAE or SAR refers to an event in which the patient was at risk of death at the time of the event; it does not refer to an event that hypothetically might have caused death if it were more severe.

^{***} Hospitalisation is defined as an in-patient admission, regardless of length of stay, even if the hospitalisation is a precautionary measure for continued observation. Hospitalisation for a pre-existing

condition, including elective procedures, which has not worsened does not constitute a serious adverse event.

Suspected Unexpected Serious Adverse Reaction (SUSAR): a SAR that is unexpected i.e. the nature or severity of the event is not consistent with the applicable product information (i.e. the SPC for capecitabine). A SUSAR should meet the definition of an AR, UAR and SAR as detailed above.

7.2 Assessment of Adverse Events

All adverse events will be graded according to the National Cancer Institute Common Terminology Criteria for adverse events (NCI CTCAE version 3.0), a copy of which will be enclosed in the Site Folder, and causality (relationship to study therapy) will be assessed. Adverse events incurred but not categorised by the NCI CTCAE should be graded by the physician and recorded using a scale of (1) mild, (2) moderate, or (3) severe on the CRF. A preexisting condition should not be reported as an adverse event unless the condition worsens or episodes increase in frequency during the adverse event-reporting period.

It is the responsibility of the local Investigator to assess seriousness and causality to protocol treatment when reporting an SAE. The Clinical Co-ordinator (or Deputy) will also be responsible for independently determining the seriousness, causality and expectedness of the event.

Causality Criteria:

Relationship	Description
UNRELATED	There is no evidence of any causal relationship
UNLIKELY	There is little evidence to suggest there is a causal relationship (e.g., the event did not occur within a reasonable time after study treatment). There is another reasonable explanation for the event (e.g., the patient's clinical condition, other concomitant treatments).
POSSIBLE	There is some evidence to suggest a causal relationship (e.g., the event occurred within a reasonable time after the study treatment). However, the influence of other factors may have contributed to the event (e.g., the patient's clinical condition, other concomitant events).
PROBABLE	There is evidence to suggest a causal relationship, and the influence of other factors is unlikely.
DEFINITE	There is clear evidence to suggest a causal relationship, and other possible contributing factors can be ruled out .

Adverse Events Monitoring & Reporting Period 7.3

All adverse events will be assessed by the Investigator and recorded onto the appropriate pages of the patient case report forms (CRFs). New toxicities in the Treatment Arm will be recorded for four weeks after the last administration of capecitabine or until the start of other anti-cancer

treatment, whichever occurs first.

All Serious Adverse Events (SAEs) occurring in both the Treatment Arm and Control Arm will

be recorded for at least 9 months post randomisation, and for at least 4 weeks after the last

administration of capecitabine (if applicable), or until the start of other anti-cancer treatment,

whichever occurs first. The Investigator will take all therapeutic measures necessary for

resolution of any adverse event. Any medication necessary for treatment of the adverse event

must be recorded onto the concomitant medications section of the patient CRF. If more that one

adverse event occurs, each event should be recorded separately.

Serious Adverse Event Reporting

For patients in both the Treatment Arm and Control Arm:

All SAEs occurring during the first 9 months post-randomisation, and for at least 4 weeks

after the last administration of capecitabine (if applicable), even if not thought to be related to

protocol treatment, must be reported in an expedited manner to the BILCAP Study Office using

the SAE form supplied in the site folder, as outlined below:

In the case of an SAE the Investigator must immediately (within 24 hours of awareness of

event):

Complete an SAE Form. This should be signed by a relevant member of the site trial

team.

Send by fax the signed and dated SAE Form to the BILCAP Study Office, along with

41

the fax cover sheet provided in the site folder:

Fax (24 Hours) [name]

(alternative [contact])

Protocol version 8, 11th July 2016 Cancer Research UK Clinical Trials Unit

- A receipt of the SAE form should be faxed back to the centre within 2 working days.
 Telephone the BILCAP Study Office to inform the Trial Co-ordinator if a fax is not received : [name]
- Telephone on day of awareness the BILCAP study office if SAE is life-threatening or fatal : [name]
- **Notify** LREC and the NHS Trust as required by local policy (there is no requirement to report SAEs to LREC unless this is part of local policy).

It is the responsibility of the sponsor or designee to report all Suspected Unexpected Serious Adverse Reactions (SUSARS) as determined by the Clinical Co-ordinator (or deputy) to the relevant regulatory authorities (e.g. Medicines and Healthcare products Regulatory Agency (MHRA) and the Multi-Centre Research Ethics Committee (MREC)) in the expedited time frame required by UK legislation. All Investigators will be notified of SUSARS on a regular basis. The BILCAP Study Office will send a safety report to the MHRA and MREC annually.

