6 PROCEDURES & CLINICAL ASSESSMENTS

6.1 Schedule of Events

Patient monitoring, blood tests, clinical and radiological assessments will be conducted as defined in the charts below. Assessments are described in more detail in the following sections.

Table 6.1 Schedule of Events for Treatment Arm

	TREATMENT ARM					
	Baseline a within 1 week prior to randomisation	Day 1 of every cycle	End of treatment (within 4 weeks of last administered capecitabine)	Follow-up post- randomisation 3 monthly (1st year)	Follow-up post- randomisation 6 monthly (2nd year)	Follow-up post- randomisation 12 monthly (3-5 years)
History	X					
Physical Examination	X	X	X	X	X	
Performance status	X	X	X	X	X	X
Weight	X	X	X	X	X	
Vital signs	X	X	X	X	X	
Haematology ^c	X	x e		x	X	
Biochemistry ^d	x	x e		x	X	
Ca19.9 measurement	X			x	X	X
CT Scan (chest, abdomen and pelvis)	x ^b			x ^g (at 6 and 12- month visits only)	x ^g	x ^g
Chemotherapy		X				
Issue Patient Diary		X				
Toxicity/Adverse Event monitoring		x f	X			
Quality of Life	X			x	X	
Symptom monitoring		X				

a Baseline assessments to be carried out within 1 week prior to randomisation, except:

b Baseline CT scan, or other adequate imaging confirmed by BILCAP office, should be performed within 4 weeks prior to surgery or within 12 weeks following surgery and before the start of treatment. If treatment start date is >12 weeks, it will be necessary to contact the BILCAP Trial Office.

c Haematology to include full blood count.

d Biochemistry to include liver function tests (AST, ALP, bilirubin), serum creatinine, urea and electrolytes.

e Haematology & biochemistry can be performed up to 5 days prior to day 1 of the treatment cycle.

f Toxicity monitoring not applicable on day 1 of the 1st cycle.

g Protocol CT scan schedule should be followed until disease recurrence is documented. After recurrence is documented CT scans to continue at Investigator's discretion and according to normal local practice.

Table 6.2 Schedule of Events for Control Arm

	CONTROL ARM				
	Baseline ^a Within 1 week prior to randomisation	Follow-up post-randomisation 3 monthly (1st year)	Follow-up post-randomisation 6 monthly (2nd year)	Follow-up post-randomisation 12-monthly (3-5 years)	
History	X				
Physical Examination	X	X	x		
Performance status	x	X	x	x	
Weight	x	X	x		
Vital signs	x	X	x		
Haematology ^c	X	X	x		
Biochemistry ^d	x	X	X		
Ca19.9 measurement	X	X	x	X	
CT Scan	X b	x e	x e	x e	
(chest, abdomen and pelvis)		(at 6 and 12-month visits only)			

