Chemotherapy					
Issue Patient Diary					
Toxicity / Adverse Event monitoring					
Quality of Life	x	X	x		
Symptom monitoring					

- a Baseline assessments are to be carried out within 1 week prior to randomisation, except:
- b Baseline CT scan, or other adequate imaging confirmed by BILCAP office, should be performed within 4 weeks prior to surgery or within 12 weeks following surgery and before the start of treatment. If treatment start date is >12 weeks, it will be necessary to contact the BILCAP Trial Office.
- c Haematology to include full blood count.
- d Biochemistry to include liver function tests (AST, ALP, bilirubin), serum creatinine, urea and electrolytes.
- e Protocol CT scan schedule should be followed until disease recurrence is documented. After recurrence is documented CT scans to continue at Investigator's discretion and according to normal local practice.

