9.3 Analysis

The primary analysis will be comparison of overall survival across treatment groups, calculated from the time of randomisation to the date of death (or censor date). All analysis will be on an intention to treat basis. Comparison of survival estimates will be by log-rank analysis. Toxicity and response rates will be compared across treatment groups using Pearson's chi-square test. QoL scores will be calculated according to the EORTC C30 manual and EuroQoL guidelines and compared across treatment groups using standardised area under the curve analyses and Mann-Whitney tests. Cox proportional hazards models will be undertaken to determine prognostic factors and their influence on survival and provide an adjusted treatment effect by important prognostic and stratification factors.

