During the last three months (i.e. since you last filled out this questionnaire), we would like you to tell us about any health problems you may have had. Please answer all the questions yourself by ticking the box that best applies to you.

THE INFORMATION YOU PROVIDE WILL BE KEPT STRICTLY CONFIDENTIAL AND USED ONLY FOR MEDICAL RESEARCH.

1. Talking to a doctor a) During the last three months ending yesterday, apart from any visit to a hospital, did you talk to a doctor, either in person or by telephone?
Yes No (if no, go straight to question 2)
If Yes: b) How many times did you talk to a doctor in these three months? (please circle)
1 2 3 4 5 6 7 8 9 or more
c) Was this consultation
under the National Health Service, or paid for privately?
d) Was the doctor: 1 a GP (i.e. a family doctor), 2 a specialist, 3 some other kind of doctor?
e) Did you talk to the doctor 1 by telephone, 2 at your home, 3 in the doctor's surgery, 4 at a health centre, 5 or elsewhere?
f) Did the doctor prescribe you any medication?
Yes No
If yes, was this prescribed for use over a short period or permanently?
Short Permanently
Please list the prescribed medication below:
Please go on to the next page

2. Hospital visits During the last three months have you had any visits to hospital for any reason?
Yes No (if no, please go to question 3)
If yes, please give details of your attendance or admittance? 1. Out-patient; how many times how many days
3. During the last 3 months has a nurse visited you at your home for any reason?
Yes No (if no, please go to question 4)
If yes, how many times?
4. During the last 3 months has anyone from social services or a voluntary organisation visited you at your home for any reason?
Yes No (if no, please go to question 5)
If yes, how many times?
5. During the last 3 months has a relative or friend taken time off work to look after you? Yes No
If yes, how many days?
If yes to any of the above questions 1 - 5, what was the problem?

THANK YOU VERY MUCH FOR COMPLETING THESE QUESTIONS.

Section 4: BILCAP Health Problems Questionnaire

For patients on follow up during the second year

During the last six months (i.e. since your last visit to hospital for follow-up), we would like you to tell us about any health problems you may have had. Please answer all the questions yourself by ticking the box that best applies to you.

THE INFORMATION YOU PROVIDE WILL BE KEPT STRICTLY CONFIDENTIAL AND USED ONLY FOR MEDICAL RESEARCH.

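### The AE definition (7.1) and the control-arm schedule (Table 6.2) do not support two-arm SAE collection (7.3), so any between-arm harm comparison is open to ascertainment bias of unknown size

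*Protocol*

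**What the plan says.** - **SAE recording, section 7.3.** The rule applies to "All Serious Adverse Events (SAEs) occurring in both the Treatment Arm and Control Arm". The minimum period is 9 months from randomisation and, for those given capecitabine, 4 weeks beyond the final dose; it ends sooner if another anti-cancer therapy begins. The SAE reporting section that follows names both arms again, includes events not thought to be related, and sets a 24-hour clock from site awareness.
- **AE definition, section 7.1.** An AE is "any untoward medical occurrence in a patient receiving treatment according to the study protocol". The SAE definition is worded separately and does not repeat that limit, but it refers to an occurrence at any dose. Section 5.3 gives controls no scheduled post-operative treatment.
- **Schedule, section 6.1.** "Patient monitoring, blood tests, clinical and radiological assessments will be conducted as defined in the charts below". In Table 6.2 (control arm) the row "Toxicity / Adverse Event monitoring" has no visit marked. In Table 6.1 (treatment arm) the corresponding row is marked on day 1 of each cycle except the first (footnote f) and at end of treatment, but at no follow-up visit.
- **Follow-up, section 6.5.** Both arms have clinical review every 3 months in year 1. Asking about SAEs is not listed.
- **Outcome and analysis.** Section 8.2 confines the toxicity outcome to the treatment arm. Section 9.3 states: "Toxicity and response rates will be compared across treatment groups using Pearson's chi-square test".
- **Questionnaire, Appendix 9, first-year version.** Both arms are asked: "During the last three months have you had any visits to hospital for any reason".

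**The concern.** The protocol asks for the same SAE data from both arms over the same window, but its definition and its visit schedule provide for that in one arm only. A site that follows the charts asks treated patients about events repeatedly during chemotherapy and has no marked occasion to ask a control. An admission of a control patient, particularly to another hospital, may never be reported.

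If capture differs between arms, an excess of reported SAEs on capecitabine can appear when the true risks are equal. The monitoring committee and the final report could then overstate the serious harm of the drug. The toxicity comparison across groups in 9.3 has the same weakness in a sharper form, because no toxicity assessment is scheduled for controls at all.

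**Working it through.** The protocol gives no figure for SAE frequency or completeness, so there is nothing to reproduce. The check is a count from the schedules, followed by an illustration under stated assumptions.

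**1. Marked adverse-event enquiries within 9 months**

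| | Treatment (Table 6.1) | Control (Table 6.2) |
|---|---|---|
| Day 1 of cycles 2 to 8 | 7 | not applicable |
| End of treatment | 1 | not applicable |
| Follow-up visits at 3, 6 and 9 months | 0 | 0 |
| Total | 8 | 0 |

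Nominal clinic contacts in the same window are 8 cycle days + 1 end of treatment + 3 follow-up = 12 for a treated patient completing all cycles, and 3 for a control.

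**2. Part of the window covered by a marked enquiry**

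Nine months is about 39 weeks. Taking treatment to start at randomisation, the treated arm is covered for 24 + 4 = 28 weeks. That leaves 39 − 28 = 11 weeks (11/39 = 28%) with no marked enquiry. For controls the uncovered part is 39/39 = 100%. The imbalance therefore comes from the cycle and end-of-treatment visits. At the common follow-up visits the two tables are alike, with nothing marked in either.

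**3. Does the rest of the text supply control data for 9.3?**

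Section 8.2 restricts toxicity to the treatment arm, section 7.3 sets a period for recording new toxicities in the treatment arm only, and Table 6.2 schedules none for controls. The cross-group toxicity test in 9.3 therefore has no planned control data behind it.

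**4. Illustration only**

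Assumptions that are not in the documents: the same true SAE risk p in both arms, full capture on capecitabine, and a fraction c captured in controls. From the protocol: 410 patients randomised equally, so n = 205 per arm.

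Apparent risk ratio = p / (p × c) = 1/c.

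Probability of a significant excess on capecitabine (two-sided 5%, normal approximation) = Φ[(d − 1.96 × s0) / s1], where d = p − pc, m = (p + pc)/2, s0 = √(2m(1 − m)/n) and s1 = √((p(1 − p) + pc(1 − pc))/n).

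For p = 0.20 and c = 0.80: d = 0.04, m = 0.18, s0 = 0.0379, s1 = 0.0379, giving Φ(−0.907) = 18.2%.

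| Control capture c | Apparent risk ratio | p = 10% | p = 20% | p = 30% |
|---|---|---|---|---|
| 100% | 1.00 | 2.5% | 2.5% | 2.5% |
| 90% | 1.11 | 5.3% | 7.4% | 9.9% |
| 80% | 1.25 | 10.5% | 18.2% | 27.7% |
| 70% | 1.43 | 19.2% | 36.5% | 55.2% |

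The table shows that modest under-capture could matter. It does not estimate what happened or will happen in this trial, and it refers to an SAE test that the protocol does not specify.

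**The case against.** The case on the other side is substantial.

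- **Control SAEs are required in plain terms.** Section 7.3 and the reporting section name the control arm, and the qualifier after capecitabine shows that untreated patients were considered. The SAE definition is not limited to treated patients, and its reference to dose cannot sensibly cancel a rule that names controls. This stands. It means the two-arm duty exists; it does not make the 7.1 wording or the empty row consistent with it.
- **The empty row may be deliberate.** In the treatment arm it serves per-cycle worst-grade toxicity (6.3 and 6.4), so a blank for controls agrees with 8.2. SAE reporting is triggered by awareness and not by a visit. This also stands in part, but awareness depends on contact and on asking, and the schedule provides far more of both in one arm.
- **Controls are not out of sight.** They are reviewed at 3, 6 and 9 months, and those in the QoL part report hospital visits in booklets that a named person at the site collects and checks. The case report forms are not shown and might carry an SAE prompt. These are real routes to awareness, although the protocol links none of them to SAE reporting.

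A reader might go further and infer that control SAEs are in fact under-counted. The points above rule that out as a finding: it is a risk and not a shown fact. A reader might also infer that the protocol plans a between-arm SAE test that is biased. It names none; the stated comparison is of toxicity, and how SAEs are tabulated may be left to the analysis plan. Nor are SAEs the only harm data comparable between arms. Haematology, biochemistry and patient-reported symptoms such as nausea, diarrhoea and sore mouth are scheduled in both.

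Last, this version is dated July 2016 and enrolment was planned to end in July 2014. On that plan the last 9-month window closed about April 2015, so a change to the visit schedule would do little for most patients.

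**Conclusion.** The inconsistency holds on the text. Sections 7.3 and the SAE reporting section require two-arm SAE collection, while the AE definition in 7.1 and the control schedule in Table 6.2 do not provide for it. Marked enquiries in the 9-month window are 8 against 0. Control SAEs are liable to be captured less completely, so a between-arm harm comparison is open to ascertainment bias, probably against capecitabine. The clearest instance in the text is 9.3, which compares toxicity across groups although 8.2 confines it to the treatment arm and no control toxicity data are scheduled.

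The size of any bias cannot be derived, because the documents give neither an SAE rate nor a capture rate. The probabilities in the illustration rest wholly on assumed values of both. The primary survival comparison is not affected.

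**What to change.** 1. **Section 7.1.** Define AE and SAE as any untoward medical occurrence in a randomised patient, in either arm.
2. **Tables 6.1 and 6.2 and section 6.5.** Mark the same SAE review at the existing 3-, 6- and 9-month visits in both arms, for any patient still inside the window.
3. **Sections 8.2 and 9.3.** Reconcile them: describe graded toxicity in the treatment arm only, and restrict the between-arm comparison of adverse events to SAEs from randomisation to 9 months, with the difference in ascertainment stated beside the result. The planned QoL comparison is unchanged.
4. **Patients already past 9 months.** In both arms, check reported SAEs against the hospital-visit answers in the 3-, 6- and 9-month questionnaires, and query in-patient admissions that have no matching report.

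Given the date of this version, items 3 and 4 are the useful parts for most patients.

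The cost is wording, some data queries and possibly more control-arm SAE forms, with no extra visits, patients or procedures. The check in item 4 reaches only QoL participants, and only while they were well enough to attend and complete the booklet, so it reduces the problem without removing it.
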